
1.2 Study Rationale and Study Design

[figure not shown]

Figure 4: Core Elements of Transition

The disparities in health outcomes during transition for EA-SCD result from a complex interplay of factors related to the patients, their families and social networks, communities, healthcare providers and systems, practice settings, and government policies. There is currently no community standard for EA-SCD transition; however, there has been a resounding request from the SCD community and stakeholders (providers, healthcare systems, insurance payors, community-based organizations (CBO's), and patients, etc.) for a standardized transition process to be established. The high ACR rates for EA-SCD have garnered significant attention, as SCD is a leading reason for readmission and increased length of stay in most hospital systems. The topic of pediatric to adult transition has been featured in regional and national forums repeatedly with increasing urgency over the past 6 years. In 2011, the American Academy of Pediatrics (AAP) in partnership with the American Academy of Family Physicians (AAFP) and the American College of Physicians (ACP) co-authored a consensus statement that provided clear guidance and a supportive decision algorithm that describes practice-based recommendations and Six Core Elements (Fig 4; 1: transition policy, 2: transition youth registry, 3: transition preparation, 4: transition planning, 5: transition and transfer of care, and 6: transition completion) that should be a part of ANY planned health care transition program for all CSHCN based on the premise that "optimal health care is achieved when individuals of all ages receive medically and developmentally appropriate care in a process that includes ensuring that high-quality, developmentally appropriate health care services are available uninterrupted as the person moves from adolescence to adulthood."28 Further expansions of the Six Core Elements of optimal transition was refined by the Got Transition/Center for Health Care Transition Improvement, which resulted in an open access comprehensive toolkit (www.gottransition.com).

A QI time-series comparative study of change was done in five large pediatric and adult academic primary care practices in the District of Columbia by the Got Transition team. Using the Health Care Transition Process Measurement Tools (pediatric and adult versions) to examine improvements in the six specific core indicators of transition performance, they found measurable improvements in all quality indicators over a 2 year QI learning collaborative that resulted in the development of a systematic clinical transition process.²⁹ Another pediatric-to-adult managed care transition pilot project for EA with chronic mental health challenges used the QI process to incorporate the "Six Core Elements of Health Care Transition (2.0)" into routine care showing significant improvement in the Transition Index and all six core elements over an 18-month

Version 6: 12/22/2022

period.³⁰ In the southeast USA, twenty- one clinical sites participated in a needs assessment reporting a formal SCD transition program (60%); process for tracking and monitoring EA-SCD through transition (62%); readiness assessment protocol (48%); transition planning process (71%); established referral network of adult providers with a protocol for transfer (52%) with only 38% having a formal process of contacting the EA-SCD three to six months after transfer and only 10% having a formal process for ongoing communication with the receiving adult provider. The Health Care Transition Process Measurement Tools (pediatric and adult versions) will be used to examine the adherence to and adoption of the Six Core Elements of Transition practice performance at 14 pediatric and adult clinical sites. The rapid Plan–Do–Study– Act (PDSA) cycles will be utilized to implement the QI process to prospectively evaluate both the process and outcome of implementing the 6 core elements.

Study Design and Outcomes:

This will be a cluster-randomized study involving 14 clinical sites with randomization occurring at the site level. All clinical sites will implement a structured education-based transition program (STE) that will be implemented across all sites using quality improvement methodology. Implementation of this STE program will be monitored for adherence to QI process and for improvement in clinical outcomes over the 5 years of the study with the goal to fully implement the standard process within the first 18-24 months and allow for 24 months of ongoing follow up. EA-SCD participants will be enrolled while still in pediatrics and must spend a minimum of 6 months and maximum of 12 months in pediatrics to allow them to benefit from the STE intervention prior to transfer to adult care where this intervention will continue. Sites will be randomized 1:1 to receive peer mentoring or no peer mentoring [PM]. Mentoring will occur through a virtual platform and include structured frequent contacts between mentor and mentee for a minimum of 30 months. Primary outcome measures include acute care reliance (reductions in acute care visits and admissions and increase in ambulatory preventative care). Secondary outcomes include improvements in transition readiness, quality of life measures including social support, dexterity with self-care, satisfaction with transition experience for EA-SCD participants and providers, and improvements in quality of care experienced.

Rationale for Structured Education Based Transition Program [STE]:

Increase in disease knowledge, independence with self-care skills, and improved pediatric and adult provider EA-SCD transition support and knowledge is a critical goal of transition readiness. Structured patient education increases disease knowledge, provides self-management skills and is effective at increasing autonomy, self-efficacy and disease self-management that reduces acute complications in juvenile diabetes. An education-based intervention tested for feasibility revealed twice as many EA-SCD in the intervention arm completing their first adult healthcare visit within 3 months of leaving pediatric care. Patient education to achieve optimal transition readiness will use a standardized module entitled the "Who, What, Where, When, Sickle Cell Transition Education Module" or other site standard SCD education. Lack site will be given a QI change package that includes details of the Six Core Elements, the QI process training, the standard education module, and supplemental resources on QI and Transition. An EA-SCD will be identified to become a member of the transition team at each clinical site to provide the patient's perspective during the QI process.

Rationale for Peer Mentoring [PM] as Comparator:

This project will compare the effectiveness of STE+PM over STE alone in improving health outcomes in EA-SCD. While most transition coordination models utilize specific education to address patient-level barriers to care (medication adherence, disease knowledge, transition readiness), they neglect the more complex societal environment within which the EA-SCD must navigate independently in adulthood.³⁵ Challenges remain with how to establish, sustain, and measure optimal support within and outside the adult medical setting to keep EA-SCD engaged in comprehensive care through the trajectory of transition. Health system-based interventions alone are inadequate to address all the needs of EA-SCD during transition, particularly with establishing social networks outside of healthcare. EA-SCD have also identified isolation as a key challenge as they navigate transition and learning from someone who has been through the process is a desirable component of a transition program.^{17,35} PM targets the social aspects of transitioning and helps model better self-management skills. The importance of PM, where an older peer with experience provides support and guidance, emerged as a desired approach repeatedly over the past year during our dialogue with patient partners. Various studies have confirmed that without sustained support, outcomes, e.g., costly hospitalizations and increased complications worsen.³⁶ PM can effectively sustain support for EA-SCD by reducing isolation and improving community engagement and self-efficacy, while modeling independent life skills without the high-cost of professional support systems.³⁷ A peer with lived experience that provides support and mentoring was considered a desired part of transition coordination by patient partners as it reduces social isolation and increases community engagement, while teaching independent life skills. PM provides the opportunity for a reciprocal relationship between two individuals with a shared experience where the more experienced "mentor" encourages and assists the less experienced "mentee" to develop his or her full potential while offering both individuals an opportunity for development and growth.³⁷ There is robust literature to support PM in assisting youth in acquiring the optimal skills, knowledge and attitudes to be more successful.³⁸ While there is little comparative evidence on the efficacy of PM for EA-SCD, previous studies have demonstrated improved EA outcomes using PM for juvenile idiopathic arthritis (JIA) and other chronic disease groups. 39-42 A waitlist pilot randomized control study of EA with JIA "iPeer2Peer Program" deployed trained mentors to provide support and self-management education over 8 weeks using Skype video calls.³⁹. Fifty percent of pairings completed the intervention, average time on calls was twice the required duration (44.72+/- 15.76 min) and participant engagement level was robust 8.53/10 (range 7-10). The Adolescent Leadership Council (ALC) mentoring program designed by Maslow et al used a group mentoring and leadership framework to promote the psychosocial development of EA with chronic physical illness focusing heavily on structured mentoring and leadership skills.²⁷ Additional studies of PM have been described and support PM as a reasonable intervention during transition. 41-45

Patient stakeholders chose a PM program that draws from the "Chronic Disease Self-Management (CDSM) Program" in combination with mentoring techniques that focus on the African American population. ⁴⁶ The conceptual models considered relied on the need for a deliberate focus that points youth toward a more positive and productive future rather than just a buddy system. ⁴⁷⁻⁴⁹ Our patient stakeholders also requested that mentors be paired with "advisors" who can provide the mentors with additional support to reduce burnout in what they referred to as the "village".

Rationale for Use of Supplemental Qualitative Methods:

The qualitative portion of the research plan is designed to supplement the original ST3P-UP study aims and will be approved as a separate protocol through Georgia Southern University. The supplemental qualitative aims will provide a viable and robust approach that will allow for evaluation of the study's processes, quality improvement, impact, and outcomes including: 1) the identification of the facilitators and barriers to enrollment of EA-SCD and mentors from multi stakeholder perspectives; 2) an assessment of mentor-mentee experiences with one-to-one peer mentoring; 3) an assessment of site experiences with the implementation of Quality Improvement methods within their clinical practices; 4) a determination of the effect of engagement activities on communication within the site triad (adult/pediatric physicians, CBOs, and patients); and 5) the development of a definition of transition success across the triad (adult/pediatric physicians, CBOs, and patients).

A deeper dive into the lessons learned related to the peer mentoring comparator within the ST3P-UP study will be gleaned from these supplemental qualitative aims.

Conceptual Model:

Based on the review of the literature on SCD Transition, the bio-psychosocial ecological model was identified as the best theoretical framework to address the comparative multi-level interventions that are needed to optimize transition outcomes in this population. This model proposes that it is necessary to examine an individual's health by considering the interactions of biology, psychology and social factors within the individual's environment to produce a more effective, multi-dimensional approach to chronic disease management. The model removes the focus from "microscopic" individual level factors (e.g. adherence, individual conduct) and broadens the view of the individual to understand "macroscopic" (communities, health care systems, etc.) influences on illness and behavior and allows practitioners to view the individual in constant interaction with their environment. Thus, we chose a health system approach to improving transition processes within the clinical setting that included individual level education. Our hypothesis is that the addition of a PM intervention that influences social interactions and the microsystem that touches the EA-SCD will be more effective than a STE-based transition program alone in improving acute care utilization.

2. STUDY OBJECTIVES

2.1 Primary Objective

The primary objective of this study is to compare the effectiveness of STE+PM versus STE at decreasing the number of acute care visits per year over a 24-month period among EA-SCD.

2.2 Secondary Objectives

Version 6: 12/22/2022

2.2.1 Patient-Reported Outcomes

To compare the effectiveness of STE+PM versus STE at improving patient-reported outcomes (PROs) among EA-SCD (Appendix A). Surveys used to evaluate PROs will include:

- Adults Sickle Cell QOC Measure (ASCQ-ME QOC) for health-related quality of life
- PedsQLTM-SCD module for health-related quality of life
- Medical Outcomes Study Social Support Survey (MOS-SSS)
- Transition Readiness Score as measured by the TIP-RFT scale
- Health Care Transition Feedback Survey for Youth and Young Adults

2.2.2 Healthcare Utilization

To compare the effectiveness of STE+PM versus STE at reducing healthcare utilization among EA- SCD.

Measures to assess healthcare utilization will include:

- The number of acute care visits per year over the entire study period
- The number of ambulatory visits per year over the entire study period
- The number of visits with adult providers over the entire study period
- The number of hospitalization days over the entire study period
- 14-day and 30-day readmissions over the entire study period

2.2.3 Intervention Fidelity (PM Intervention Feasibility)

- Number of consented mentor candidates that complete each step of eligibility and training activities
- Timelines for major milestones for mentors
- Time from consent to enrollment for EA-SCDs
- Frequency of mentor-EA-SCD contacts via the platform

2.2.4 ST3P-UP Application Usage

- Frequency of contacts between study subjects (EA-SCD, Mentor, or Advisor) and transition coordinator
- Frequency of contacts between investigators and transition coordinators
- Frequency of contacts between investigators
- Frequency of education resource views from application

2.3 Exploratory Objectives

- Evaluate the adoption of and adherence to the Six Core Elements of transition practice performance at each site.
- Identify through a modified Delphi process and other qualitative research methods the patient and stakeholder determined optimal outcome(s) of transition and compare to predetermined outcome of acute care reliance.

2.4 Qualitative Research Objectives

- Determine the facilitators and barriers to enrollment of EASCDs and mentors from multi stakeholder perspectives.
- Describe mentor-mentee experiences with one-to-one peer mentoring.

Version 6: 12/22/2022

• Assess site triad experiences with implementing quality improvement within their clinical practices.

- Determine the effect of engagement activities on communication within the site triad (adult/pediatric physicians, CBOs, patients).
- Develop a multi-stakeholder, ecologically focused definition of transition success.

3. SUBJECT SELECTION

3.1 Subject Identification and Recruitment

EA-SCD Subject Recruitment

EA-SCD subjects will be recruited at Atrium Health and other participating institutions. Recruitment will include patients with SCD 16 to 25 years of age who are currently receiving care in a pediatric SCD program. Recruitment will include both males and females, and all race and ethnicity classifications.

Mentor Subject Recruitment

Mentor subjects will be recruited at Atrium Health and other participating institutions. Recruitment will include individuals with SCD age 26 years or older receiving care from an adult SCD provider. Recruitment will include both males and females, and all race and ethnicity classifications.

Advisor Subject Recruitment

Advisor subjects will be recruited at Atrium Health and other participating institutions. Recruitment will include individuals with SCD age 36 years or older receiving care from an adult SCD provider. Recruitment will include both males and females, and all race and ethnicity classifications.

Qualitative Participant Recruitment

Sites will be provided the IRB approved Qualitative Participant Recruitment script to ask participants for permission to share their names with Georgia Southern University faculty. Participant names will be entered into REDCap (Atrium Health's Secure Electronic Data Capture System). Sites will document a yes/no response from the participant in REDCap.

3.2 EA-SCD Eligibility

3.2.1 Inclusion Criteria

Subject must meet all the following applicable inclusion criteria to participate in this study:

Version 6: 12/22/2022

1. Informed consent signed by subject or parent/ guardian (where applicable) and HIPAA authorization for release of personal health information. NOTE: HIPAA authorization may be included in the informed consent or obtained separately.

- 2. Assent will be obtained in appropriately aged subjects per IRB or institutional guidelines.
- 3. Age ≥ 16 and ≤ 25 years at the time of consent AND being cared for in a PEDIATRIC SICKLE CELL PROGRAM
- 4. Any sickle cell genotype
- 5. Not known to be currently pregnant
- 6. Readily available access to a computer with internet and phone
- 7. Ability to read and understand the English language
- 8. Subject is planned to be transferred to an adult sickle cell program within 6 -12 months of consent. If an EASCD subject, at a peer mentor site, is reconsented due to a delay in matching the EASCD subject must continue to meet eligibility from the date of reconsent.

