Transition from pediatrics to adult care is a critical time for EA-SCD. The emergency department (ED) becomes a primary source for care, with ED visits and admissions per year doubling, and avoidable acute care visits rising to account for two-thirds of all SCD hospitalizations. ^{8,11,12} Data from the Healthcare Cost and Utilization Project State Inpatient Databases and State Emergency Department Databases from eight states showed that EA-SCD (18–30y) had the highest acute care utilization rates compared to children 10-17y (3.61 vs 2.04 visits/patient/year). ¹³ The 30-day readmission rate doubled from 27.4% to 48.9% respectively. ¹³ Data from the Registry and Surveillance for Hemoglobinopathies (RuSH) Project cite an increase in acute care utilization rates among EA-SCD (Fig 1). In GA, utilization rose from 0.8 to 3.0/person/year among individuals 10-19y of age compared to those 20 - 49y. ¹⁴ In NC, the average annual acute care visits per person increased from 5 in those <18 years to 12 among 18-35y. ⁴ Disparities also exist with school absenteeism, and EA-SCD miss an average of 20-40 school days/year due to illness, have worse standardized test scores, higher rates of repeat grades and lower overall school attainment compared to controls. ¹⁵ There is limited research to support evidence-based interventions that effectively reduce the high mortality, morbidity, and poor QOL during transition.

Barriers to Transition:

Several identified patient, provider and health system factors contribute to the poor health outcomes of EA-SCD during transition. ¹⁶⁻¹⁸ EA-SCD struggle emotionally with adjusting from a more paternalistic pediatric model to the adult "individualistic" model of care. Adherence to disease modifying treatment drops significantly as they struggle with the developmental maturation process. ¹⁹ Changes or lapses in insurance lead to gaps in comprehensive care -

Version 6: 12/22/2022

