specialized and primary - during transition, amplifying existing barriers to accessing crucial services as disease burden is increasing. 20,21 A retrospective study showed that patients who are transitioning received 46% fewer transfusions by age 22y compared to children and were 4.7 times less likely to receive iron chelation by age 25y. 21 At Atrium Health (formerly known as Carolinas Healthcare System), a large healthcare system in the SE US that provides care for 1300 adults and 400 children with SCD, only 8-14% of EA-SCD accessed a scheduled visit with their primary care/SCD provider in 2015 with mean acute care reliance (ACR; number of acute care visits per year/ [all acute care visits + all ambulatory care visits]) rates of 42% (Fig 2). Mean acute care visits/year rose significantly from 2.1 ± 2.9 among 16- 18y to 4.2 ± 6.8 among 19 - 21y and was highest among 21 - 25y at 5.3 ± 8.5 (p<0.01). ACR (\geq 0.33) is an indicator of inadequate access to primary and preventative care. 22 EA-SCD report having inadequate information about adult care and a poor understanding of their disease and how it becomes more complex with age. $^{14, 16}$ There are significant knowledge gaps and poor communication between pediatric and adult providers that worsen the problem created by a lack of standardized EA-SCD patient education curriculum.

Limited evidence on effective transition programming:

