e - ST3P-UP App contains "Who, What, Where, When" Sickle Cell Transition Education Modules that are required for 3-month visits. If app is not available, the education modules are provided to the sites in the QI Change Package and via PowerPoint from the DCC. Alternatively, sites can utilize any standard SCD education module.

- f Patients are encouraged but not required to download the ST3P-UP App. Directions to access the ST3P-UP app and instructions for use will be provided to participants by local site Transition Coordinators. Transition Coordinators are encouraged to use study- provided tablets and/or iPads to facilitate follow-up visit adherence communication and for structured transition education.
- g For PM sites, mentee availability should be captured in the REDCap database at the time of consent. For subjects with delayed enrollment, confirmation of availability should be revisited at the time of Mentor-Mentee matching.
- h Every effort should be made to complete the baseline survey within a healthcare setting but if administration occurs via survey link, this must be provided to the participant within 72 hours from the date of consent (for the STE arm) or from the date of match (for the PM arm). The survey link will expire within 2 weeks of receipt. If the survey remains incomplete after two weeks, please discontinue efforts to contact the participant for completion of the baseline survey.

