10.1.2 Enrollment Date

EA-SCD Participants:

The date the baseline survey is administered to a subject (either within a healthcare setting or via survey link).

For participants on the PM arm, administration of the baseline survey and completion of the enrollment CRF occurs after confirmation of mentor matching from the DCC (see study calendar 6.3).

Mentor and Advisor Participants:

The date the participant completes all training activities. For mentors, this is the date the participant completes practice call 2. For advisors, this is the date the participant completes Peer Mentor University training.

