10.5.4 Primary Analysis

To evaluate the impact of PM, the acute care utilization rate per year will be compared between the PM+STE and STE arms. This will be accomplished using generalized linear mixed model with a Poisson distribution-log link construct. The model will include fixed effects for baseline acute care visits per year, the stratification factor (large sites vs small sites) and treatment arm, and a random effect for clinical site. Corresponding 95% confidence intervals will be calculated for the estimated ACU rate in each treatment arm.

Supportive and sensitivity analyses will be conducted to include potential confounding factors such as urban versus rural sites, education level, older first degree relative with SCD, genotype, age at transfer to adult care, and type of receiving provider (primary versus specialty). Univariate models will be fit for each factor, and those identified to be individually prognostic will be included in a multivariable model, and backward elimination followed by forward selection will be used to identify factors that are independently prognostic and to establish a final base model. Finally, treatment arm will be added to the base model to evaluate the impact of the intervention adjusting for significant baseline factors.

Two analyses will be conducted to estimate the impact of differential accrual between arms over time: (1) An additional term of year of enrollment will be added to the GLMM as a categorical variable; (2) We will subset the analyses to EA-SCD who were contemporaneously enrolled. Comparison of the PM+STE and STE ACU estimates from this subset to those results including all enrolled with and without controlling for year of enrollment will provide a comprehensive assessment of the potential bias due to differential accrual between arms over time. ACU rate in the STE only arm will be compared to historical ACU rates which were used for the original power calculations. Although these are comparisons to historical controls, this will provide preliminary evidence using a robust sample size of the potential impact of the structure transition education.

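### Planned transfer is timed from consent but follow-up from enrollment, which on the PM arm waits for a mentor match, so the arms can contribute different mixes of pre- and post-transfer time without adjustment

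*Combined protocol and SAP*

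**What the plan says.** **Transfer.** Section 3.2.1, criterion 8: "Subject is planned to be transferred to an adult sickle cell program within 6 -12 months of consent". For a PM-site participant who is reconsented because matching was delayed, it adds that "the EASCD subject must continue to meet eligibility from the date of reconsent".

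**Outcome clock.** In section 10.3.1, months on study run from the enrollment date to the off-study date. Section 10.1.2 defines enrollment as "The date the baseline survey is administered to a subject", and adds: "For participants on the PM arm, administration of the baseline survey and completion of the enrollment CRF occurs after confirmation of mentor matching". Note h to the calendar in section 6.3 requires a baseline survey sent by link to go out "within 72 hours from the date of consent (for the STE arm) or from the date of match (for the PM arm"). Under section 7.1, participants still enrolled when the funded project ends go off study on that date.

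**Pediatric period.** Section 1.2 requires 6 to 12 months in pediatrics. Section 5 has enrolled subjects tracked for at least 6 months in pediatrics and at least 24 months in adult care.

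**Expected course.** Section 1.1 describes transition as a time "with ED visits and admissions per year doubling". From one health system it reports: "Mean acute care visits/year rose significantly from 2.1 ± 2.9 among 16- 18y to 4.2 ± 6.8 among 19 - 21y".

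**Analysis.** Section 10.5.4: "The model will include fixed effects for baseline acute care visits per year, the stratification factor (large sites vs small sites) and treatment arm", plus a random effect for site. The baseline count covers the 12 months before enrollment (section 6.4.2). The checks for differential accrual use year of enrollment and a contemporaneously enrolled subset. Age at transfer is one candidate covariate in the supportive models.

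**The concern.** Two anchors are in use. Transfer is planned from consent and exposure is counted from enrollment. On the STE arm these nearly coincide; on the PM arm they are separated by the wait for a mentor. A PM participant who waits, and is not reconsented, uses up pre-transfer months before the clock starts. Over the same length of follow-up, that person contributes fewer pediatric months and more adult months than an STE counterpart.

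If acute visits rise at transfer, that difference enters the arm contrast even when mentoring does nothing and nobody is lost while waiting. It is a shift of time origin, separate from the question of who gets enrolled. Year of enrollment and the contemporaneous subset address calendar time, not distance to transfer. Age at transfer does not give that distance either.

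The protocol expects waits: criterion 8 refers to delayed matching, note g in section 6.3 to delayed enrollment, and section 10.3.3 reports time from first consent to enrollment on the PM arm. It gives no expected or maximum wait for mentees. The 90-day limit in section 5.2.3 applies to mentors and advisors.

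**Working it through.** **The plan's own figures.** The plan gives no figure for this bias. Its sample size reproduces and serves as the base for power.
- Individual randomization, rates 6 and 4.8 per year: n = (1.960 + 1.036)² × (6 + 4.8) / 1.2² = 67.3 per arm (plan: 67).
- Seven sites per arm, cluster-size coefficient of variation 0.60, ICC 0.05: design effect DE = 1 + [(1 + 0.60²)n/7 − 1] × 0.05. Solving n = 67 × DE gives 182.3 (plan: 183).
- At 269 per arm, DE = 3.563 and power is about 89%.

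**Inputs for the bias.**
- T, months from consent to transfer: 9, the middle of the 6-12 window.
- d, the PM wait: 1, 3 or 6 months, **assumed**.
- R, post- to pre-transfer rate ratio: 2, from the doubling in section 1.1 and from 4.2/2.1. A step exactly at transfer is **assumed**.
- F, months on study; true rate ratio 0.80; no reconsent.

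**Formula.** An arm's mean rate, in units of the pre-transfer rate, is [(T − d) + R(F − T + d)]/F, with d = 0 for STE. The apparent rate ratio is 0.80 × (PM value, without a mentoring effect) / (STE value).

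**(a) 24 months in total, both arms.** STE: (9 + 2×15)/24 = 39/24.

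**(b) 24 adult months, both arms**, as section 5 intends. STE: (9 + 2×24)/33 = 57/33 = 1.727.

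| Wait | (a) PM ÷ STE | (a) apparent ratio | (b) PM ÷ STE | (b) apparent ratio |
|---|---|---|---|---|
| 1 month | 40/39 = 1.026 | 0.821 | (56/32)/1.727 = 1.013 | 0.811 |
| 3 months | 42/39 = 1.077 | 0.862 | (54/30)/1.727 = 1.042 | 0.834 |
| 6 months | 45/39 = 1.154 | 0.923 | (51/27)/1.727 = 1.094 | 0.875 |

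**Range.** Section 1.1 also gives 3.61/2.04 = 1.77 and 12/5 = 2.4. Over R = 1.77 to 2.4 and T = 6 to 12, a 3-month wait gives 0.825 to 0.882 across rules (a), (b) and 30 months in total.

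**Unequal follow-up.** With STE at 30 months, its value is (9 + 2×21)/30 = 1.70.
- PM with d = 3 and 18 months: (6 + 2×12)/18 = 1.667, apparent ratio 0.784.
- PM reconsented at the match (d = 0) with 24 months: 39/24 = 1.625, apparent ratio 0.765.
- At d = 3 the sign changes where (2F − 6)/F = 1.70, which is F = 20 months.

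**Power.** This uses the normal approximation with the design effect above, STE rate held at 6 and 269 per arm. Under (a), power falls from 89% to 81% (1 month) and 58% (3 months). Under (b) with 3 months, the PM rate is 6 × 0.834 = 5.00, the difference is 0.998 and its standard error is √(11.00 × 3.563/269) = 0.382. Then 0.998/0.382 − 1.96 = 0.65, or about 74%.

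**The case against.** The case against has several parts.

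- **Reconsent.** The sentence after the transfer window makes a reconsented participant meet eligibility afresh, which restarts the window. Section 12.2 refers reconsent to the central IRB's policy. This stands as a limit: the problem is confined to waits without reconsent and any gap between reconsent and match. It does not remove the problem, because the protocol does not say when a mentee's delay requires reconsent.
- **Pediatric minimum.** Sections 1.2 and 5 intend at least 6 pediatric months. Counted from enrollment, the 6-month wait, which leaves 3, would breach that. But the criterion that operates is anchored at consent and cannot secure the minimum after a wait.
- **The rates are age bands.** The figures 2.1 and 4.2, and 2.04 and 3.61, compare ages, not time before and after transfer, and pediatric patients up to 25 are eligible. A gradual rise would be partly absorbed by the look-back, which moves with enrollment. This stands; the figures are illustrations.
- **Visibility.** The PM wait will be reported (section 10.3.3). That shows its length but does not adjust the arm contrast.

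A reader might infer that a true PM benefit will be understated. The documents do not support that as a fact. Follow-up ends at study completion, section 10.5.4 itself anticipates differential accrual, and shorter PM follow-up can turn the bias the other way.

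**Conclusion.** The point holds in conditional form. The anchors differ, only the PM arm has a wait built in before its clock starts, and no planned analysis accounts for distance to transfer. If acute visits rise at transfer and delayed participants are not all reconsented at the match, the arm contrast can be biased: toward understating PM when follow-up is equal, possibly toward overstating it when PM follow-up is shorter.

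For a 3-month wait and a doubling, a true 20% reduction appears as about 14% over 24 months in total, or about 17% with 24 adult months in both arms. For 1 month it appears as about 18% or 19%. These sizes rest on an assumed wait, an assumed step at transfer and a common interval from consent to transfer in both arms. They are not estimates of the bias that will occur. If one anchor applied in both arms and follow-up were equal, the bias from this source would be nil. Because the design targets a 20% effect, even the smaller figures justify a pre-specified analysis.

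**What to change.** 1. **Data.** Record the planned transfer date at consent, and again at any reconsent. Criterion 8 already requires sites to judge that transfer falls in the window.
2. **Section 10.5.4.** Pre-specify a sensitivity analysis of the primary model that splits each participant's person-time at the planned transfer date and includes a pre/post-transfer term. This also deals with unequal follow-up. The alternative is to adjust for months from enrollment to planned transfer. The plan should then state that on the PM arm this covariate is the planned interval minus the matching wait, so it depends on the arm and is not fixed at consent.
3. **Optional.** Add an analysis that starts the clock at consent in both arms. State that it covers only those later enrolled, includes unmentored waiting time on PM, and needs dated look-back visits with an annualized pre-consent baseline.
4. **Text.** Reconcile sections 1.2, 3.2.1, 5 and 10.1.2 on the point from which the pediatric period is counted, and state when a delayed match requires a mentee to be reconsented.

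The cost is one extra field, some error in planned dates, the need to place visits before or after a date, and modest extra analysis. The primary model itself need not change.
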